### 3. OBJECTIVES

#### 3.1. Primary objectives

- To assess the reactogenicity and safety of each vaccine dose throughout the entire study period, in all study groups.
- To describe the anti-H1 stalk humoral immune response 28 days after each priming dose (1 or 2 dose(s)) in all study groups.

#### 3.2. Secondary objectives

- To evaluate the adjuvant effect of AS03 and AS01 on the humoral immune response after 1 and 2 priming dose(s) of investigational SUIVs when compared to the non-adjuvanted formulations.
- To describe the persistence of the anti-H1 stalk humoral immune response after each priming dose (1 or 2 dose(s)) in all study groups up to Month 14.
- To describe the humoral immune response after a booster dose at Month 14.
- To describe the breadth of the humoral immune response after each vaccination in all study groups.
- To describe the effect of the chimeric hemagglutinin (HA) vaccination-sequence on the humoral immune response.

#### 3.3. Tertiary objectives

- To explore the cell-mediated immune responses (B-cells and T-cells).
- To explore the immune response against the HA head of cH5/1N1 **and** cH8/1N1 strain by hemagglutination inhibition (HI) assay.
- To explore the protective effect of the stalk-reactive antibodies induced by vaccination in a passive transfer challenge experiment in mice.

**Note:** the passive transfer experiment will be analyzed by the pre-clinical statistical team and is not covered by the present SAP document.

- To develop assays for evaluation/characterization of the humoral and cellular immune responses to the investigational vaccines.
- To explore anti-stalk antibody functionality, e.g. antibody-dependent cell-mediated cytotoxicity (ADCC).

## 4. ENDPOINTS

### 4.1. Primary endpoints

#### Reactogenicity and safety

- Occurrence of solicited local and general AEs after each vaccination:
  - Occurrence of solicited local AEs during a 7-day follow-up period (i.e. on the day of vaccination and 6 subsequent days) after each vaccine dose, in all vaccine groups.
  - Occurrence of solicited general AEs during a 7-day follow-up period (i.e. on the day of vaccination and 6 subsequent days) after each vaccine dose, in all vaccine groups.
- Occurrence of unsolicited AEs after each vaccination:
  - Occurrence of unsolicited AEs during a 28-day follow-up period (i.e. on the day of vaccination and 27 subsequent days) after each vaccine dose, in all vaccine groups.
- Occurrence of hematological and biochemical laboratory abnormalities after each vaccination:
  - Any hematological (red blood cells, white blood cells and differential count, platelets count and hemoglobin level) or biochemical (alanine aminotransferase, aspartate aminotransferase, creatinine, blood urea nitrogen [BUN] and BUN-to-creatinine ratio) laboratory abnormality at each visit subsequent to Day 1, in all vaccine groups.
- Occurrence of medically attended events (MAEs), potential immune-mediated diseases (pIMDs) and SAEs:
  - Occurrence of MAEs, pIMDs and SAEs throughout the entire study period, in all vaccine groups.

#### Immunogenicity

*Anti-H1 stalk immune response measured by ELISA and by micro-neutralization (MN) assay 28 days after each priming dose:*

- Levels of anti-H1 stalk antibody titers by ELISA and by MN assay.

The following aggregate variables will be calculated for the above parameters with 95% confidence interval (CI):

- Seropositivity rates and geometric mean titers (GMTs) at Days 1, 29 and 85.
- Percentage of subjects with a  $\geq$  4-fold increase from Day 1 to Days 29 and 85.
- Percentage of subjects with a  $\geq$  10-fold increase from Day 1 to Days 29 and 85.
- Mean geometric increase (MGI) from Day 1 to Days 29 and 85.

## 4.2. Secondary endpoints

### Immunogenicity

*Adjuvant effect on the anti-stalk immune response in terms of:*

- GMT group ratio for anti-stalk ELISA titer SUIV+AS03 or AS01/SUIV non-adjuvanted, 28 days post vaccination (i.e. at Day 29 to evaluate the adjuvant effect post-dose 1 and at Day 85 to evaluate the adjuvant effect post-dose 2).

*Anti-H1 stalk immune response measured by ELISA and by MN assay after each dose:*

- Levels of anti-H1 stalk antibody titers by ELISA post-each vaccination.

The following aggregate variables will be calculated for the above parameters with 95% CI:

- Seropositivity rates and GMTs at Days 1, 29, 85, Month 8, Month 14, Month 14 + 28 days, Month 20 and Month 26.
- Percentage of subjects with a  $\geq$  4-fold increase in antibody titers by ELISA from Day 1 to each subsequent timepoint listed above.
- Percentage of subjects with a  $\geq$  10-fold increase in antibody titers by ELISA from Day 1 to each subsequent timepoint listed above.
- MGI in antibody titers by ELISA from Day 1 to each subsequent timepoint listed above.

- Levels of anti-H1 stalk antibody titers by MN assay post-each vaccination.

The following aggregate variables will be calculated for the above parameters with 95% CI:

- Seropositivity rates and GMTs at Days 1, 29 **and** 85.
- Percentage of subjects with a  $\geq$  4-fold increase in antibody titers by MN assay from Day 1 to each subsequent timepoint listed above.
- Percentage of subjects with a  $\geq$  10-fold increase in antibody titers by MN assay from Day 1 to each subsequent timepoint listed above.
- MGI in antibody titers by MN assay from Day 1 to each subsequent timepoint listed above.

*Breadth of the immune response:*

- Levels of anti-H2 and anti-H18 antibody titers by ELISA.

The following aggregate variables will be calculated for the above parameters with 95% CI:

- Anti-H2 and anti-H18 seropositivity rates and GMTs at Days 1, 29, 85, Month 8, Month 14, Month 14 + 28 days, Month 20 and Month 26.
- Percentage of subjects with a  $\geq$  4-fold increase in anti-H2 and anti-H18 antibody titers from Day 1 to each subsequent timepoint listed above.

- Percentage of subjects with a  $\geq$  10-fold increase in anti-H2 and anti-H18 antibody titers from Day 1 to each subsequent timepoint listed above.
- MGI in anti-H2 and anti-H18 antibody titers from Day 1 to each subsequent timepoint listed above.
- Levels of antibody titers by MN assay for H1N1 swine influenza and IIV4 H1N1 vaccine strains.

The following aggregate variables will be calculated for the above parameters with 95% CI:

- Seropositivity rates and GMTs at Days 1, 29 **and** 85.
- Percentage of subjects with a  $\geq$  4-fold increase in antibody titers from Day 1 to each subsequent timepoint listed above.
- Percentage of subjects with a  $\geq$  10-fold increase in antibody titers from Day 1 to each subsequent timepoint listed above.
- MGI in antibody titers from Day 1 to each subsequent timepoint listed above.

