### 6.2.3. Between group assessment

#### 6.2.3.1. ANCOVA modelling

The anti H1 HA stalk ELISA titers will be modelled using an ANCOVA model. Twenty-eight days post priming/post booster  $\log_{10}$ (titers) will be modelled as a function of the adjuvant (AS01, AS03, no adjuvant) and of the priming sequence (cH8/1N1, cH5/1N1, cH8/1N1 and cH5/1N1), including the pre-vaccination titer as covariate. The primary analysis will not include any interaction term.

For the parameter related to the priming sequence, in absence of a reference group, the overall test of difference (to reject the null hypothesis of no difference) will be done at significance level 0.10. If the test is statistically significant at level 0.10, the different pairwise comparisons will be performed at the same alpha level.

For the parameter related to the adjuvant, the pairwise comparisons to the non-adjuvant reference group (AS01 vs no adjuvant and AS03 vs no adjuvant) are planned to be performed without preamble\*. Therefore, a Dunnett test will be used for the pairwise comparisons.

\* The pairwise comparisons for the adjuvant effect will both be performed without any preliminary step (e.g. hierarchical testing) being involved. Multiplicity is being accounted for through the use of the Dunnett test.

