#### 6.2.3.2. Descriptive assessment

GMT ratios and their 2-sided 95% CI will be computed after fitting an ANCOVA model on the  $\log_{10}$  transformation of ELISA/MN titers, including vaccine group as fixed effect and the pre-vaccination titer as covariate.

Differences in percentage of subjects with a fold increase from baseline and their 95% CIs will be calculated.

Generally speaking, the 4 weeks post-dose results will be compared.

The following group ratios/differences will be provided:

- Evaluation of the proof of principle:
  - cH8/5/11-AS03 vs IIV4.
  - cH8/5/11-AS01 vs IIV4.
  - cH8/5/11 vs IIV4.
- Evaluation of the number of priming doses:
  - cH8/5/11-AS03 vs cH8/P/cH5-AS03.
  - cH8/5/11-AS01 vs cH8/P/cH5-AS01.
  - cH8/5/11 vs cH8/P/cH5

- Assessment of the adjuvant systems:
  - cH8/5/11-AS03 vs cH8/5/11-AS01.
  - cH8/P/cH5-AS03 vs cH8/P/cH5-AS01.
  - cH5/P/cH8-AS03 vs cH5/P/cH8-AS01.
- Description of the priming sequence:
  - cH8/P/cH5-AS03 vs cH5/P/cH8-AS03.
  - cH8/P/cH5-AS01 vs cH5/P/cH8-AS01.

Additional ratios/differences might be considered if deemed necessary at the time analysis.

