## 7. ANALYSIS INTERPRETATION

Comparative analyses will be descriptive with the aim to characterize the difference in reactogenicity/immunogenicity between groups.

With respect to the secondary objective and decision rule linked to the use of an adjuvant, the interpretation will be done according to the CI for the ELISA anti-stalk group GMT ratios (pooled AS01 vs pooled non-adjuvanted and pooled AS03 vs pooled non-adjuvanted) as measured 28 days after the last planned priming dose. The use of the adjuvant (AS01 or AS03) will be considered justified if the lower limit of the 94.46% CI of the group GMT ratio (adjuvanted vs non adjuvanted) is >1.50.

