## 12. ANNEX 1 STANDARD DATA DERIVATION RULE AND STATISTICAL METHODS

### 12.1. Statistical Method References

The exact two-sided 95% CIs for a proportion within a group will be the Clopper-Pearson exact CI [Clopper CJ, Pearson ES. The use of confidence or fiducial limits illustrated in the case of binomial. *Biometrika*. 1934; 26: 404-413].

The standardized asymptotic two-sided 95% CI for the group difference in proportions is based on the method described in the following paper: Robert G. Newcombe, interval estimation for the difference between independent proportions: comparison of eleven methods, *Statist Med*. 1998; 17, 873-890]. The standardized asymptotic method used is the method six.

The 95% CIs of the group GMT ratios will be computed using an ANCOVA model on the logarithm10 transformation of the titers. The ANCOVA model will include the vaccine group as fixed effects and the logarithm10 transformation of titers at Day 1. For the evaluation of adjuvant of preferred priming sequence, the vaccine group will be replaced by 2 fixed effects: the adjuvant type (AS01, AS03, No adjuvant) and the number of priming doses (1 priming dose with cH8/1N1, 1 priming dose with cH5/1N1, 2 priming doses with cH8/1N1 and cH5/1N1).

The 95% CI for GMTs will be obtained within each group separately. The 95% CI for the mean of log-transformed titer will be first obtained assuming that log-transformed values were normally distributed with unknown variance. The 95% CI for the GMTs will then be obtained by exponential-transformation of the 95% CI for the mean of log-transformed titer.

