**Template 36 ANCOVA model for <Antibody> concentration 28 days post-priming dose(s) <cohort name>**

Source	DF (numerator)	DF (denominator)	F value	p-value
Priming sequence				
Adjuvant				

Priming sequence= different types of priming sequence - <number of modalities> modalities (<each modality>)

Adjuvant = different types of Adjuvant - <number of modalities> modalities (<each modality>)

ANCOVA model on the log-transformed concentration with the pre-vaccination log-transformed concentration as regressor, priming sequence content and Adjuvant as fixed effects

DF = degrees of freedom

Main factors (Priming sequence, Adjuvant) considered as statistically significant if p-value <0.100 (model excluding interaction)

**Template 37 Dunnett's t test for the comparison of each adjuvant against the control in terms of <Antibody> concentration 28 days post-priming dose(s) <cohort name>**

Comparison	GMC ratio	p-value	94.46% CI*	
			Lower limit	Upper limit
AS01-Non adjuvanted				
AS03-Non adjuvanted				

AS01= Pooling of results at Day 29 of ch8/P/ch5-AS01, Day 29 of ch5/P/ch8-AS01 and Day 85 of ch8/5/11-AS01

AS03= Pooling of results at Day 29 of ch8/P/ch5-AS03, Day 29 of ch5/P/ch8-AS03 and Day 85 of ch8/5/11-AS03

Non adjuvanted= Pooling of results at Day 29 of ch8/P/ch5, Day 29 of ch5/P/ch8 and Day 85 of ch8/5/11

\*Comparison performed using a 2-sided alpha=0.1 and Dunnett adjustment for multiple comparisons, resulting in an adjusted alpha=0.0554

The use of the adjuvant (AS01 or AS03) is considered justified if the lower limit of the 94.46% CI of the GMC ratio (adjuvanted versus non adjuvanted) is > 1.50

**Template 38 Pairwise comparisons of priming sequences in terms of <Antibody> concentration 28 days post-priming dose(s) <cohort name>**

Comparison	GMC ratio	p-value	90% CI	
			Lower limit	Upper limit
1 priming dose (cH8/1N1)-1priming dose (cH5/1N1)				
1 priming dose (cH8/1N1)-2priming doses (cH8/1N1 and cH5/1N1)				
1 priming dose (cH5/1N1)-2priming doses (cH8/1N1 and cH5/1N1)				

1 priming dose (cH8/1N1) = Pooling of results at Day 29 of cH8/P/cH5-AS01, Day 29 of cH8/P/cH5-AS03 and Day 29 of cH8/P/cH5

1 priming dose (cH5/1N1) = Pooling of results at Day 29 of cH5/P/cH8-AS01, Day 29 of cH5/P/cH8-AS03 and Day 29 of cH5/P/cH8

2 priming doses (cH8/1N1 and cH5/1N1) = Pooling of results at Day 85 of cH5/11-AS01, Day 85 of cH8/5/11-AS03 and Day 85 of cH8/5/11

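### The by-dose adjuvant endpoint (Day 29 and Day 85) has no pre-specified direct ratio or confidence interval; the only adjuvanted versus non-adjuvanted contrast averages over both

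*SAP*

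**What the plan says.** SAP section 3.2 sets a secondary objective on the adjuvant effect of AS03 and AS01 after one and after two priming doses, against the non-adjuvanted formulations. Section 4.2 turns this into a ratio of anti-stalk ELISA GMTs, taken "at Day 29 to evaluate the adjuvant effect post-dose 1 and at Day 85 to evaluate the adjuvant effect post-dose 2".

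The analysis is set out in four places:

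- Section 6.2.3.1 models the log10 titre 28 days after priming on adjuvant, priming sequence and pre-vaccination titre, and adds: "The primary analysis will not include any interaction term".
- Section 12.1 says of the same model that "the vaccine group will be replaced by 2 fixed effects", namely adjuvant type and priming regimen.
- Template 37 gives one row per adjuvant. The AS01 row is defined as "Pooling of results at Day 29 of ch8/P/ch5-AS01, Day 29 of ch5/P/ch8-AS01 and Day 85 of ch8/5/11-AS01". The AS03 row and the non-adjuvanted reference are built the same way.
- Section 7 bases the decision on "pooled AS01 vs pooled non-adjuvanted and pooled AS03 vs pooled non-adjuvanted". An adjuvant is considered justified if the lower 94.46% limit exceeds 1.50.

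The group ratios listed in section 6.2.3.2 compare two-dose groups with IIV4, two doses with one, one adjuvant with the other (for example "cH8/5/11-AS03 vs cH8/5/11-AS01"), and one priming antigen with the other. None sets an adjuvanted group against the same schedule without adjuvant.

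**The concern.** The endpoint asks for two quantities per adjuvant and the specified analysis returns one. An additive model gives a single adjuvant effect for all three priming sequences. If the effect is much the same after one and two doses, little is lost. If it differs, the average describes neither schedule, and no specified output would show the difference with its uncertainty.

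The number of priming doses is itself under study in section 6.2.3.2, so a team choosing a schedule would want the adjuvant effect for that schedule. The plan's section 7 conclusion would be worded for the adjuvant as such.

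**Working it through.** **Reproducing the plan's own figure.** Template 37 states an adjusted alpha of 0.0554. Nine SUIV groups of 47 give 423 subjects. The model has 6 parameters (intercept, 2 for adjuvant, 2 for sequence, 1 covariate), so df = 423 − 6 = 417. For two comparisons with a shared control (correlation 0.5) and family-wise two-sided alpha 0.10, the Dunnett critical value is 1.921. The per-comparison alpha is 0.0554, which gives a 94.46% interval. The figure reproduces, so the multiplicity arithmetic is not in question.

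**What the pooled ratio estimates.** Each adjuvant level has 3 × 47 = 141 subjects: two one-dose groups read at Day 29 and one two-dose group read at Day 85. In the balanced additive model the adjuvant effect on the log scale is the plain mean over the three sequences. If both one-dose groups share the ratio R29 and the two-dose group has R85:

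pooled ratio = R29^(2/3) × R85^(1/3)

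A least-squares fit to simulated data with R29 = 3.0 and R85 = 1.0 returned 2.08 for each adjuvant, as the formula gives.

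**Lower limit.** Lower limit = ratio / 10^(1.921 × SD × √(2/n)). The SAP gives no SD, so a residual log10 SD of 0.30 to 0.50 is assumed. For n = 141 the divisor is 1.171, 1.235 and 1.301 at SD 0.30, 0.40 and 0.50. For n = 47 it is 1.315 and 1.578 at SD 0.30 and 0.50.

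**Illustrations.** The ratios are assumed, and are treated as the observed estimates.

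| R29 | R85 | Pooled | Lower limit, SD 0.30 | SD 0.40 | SD 0.50 |
|---|---|---|---|---|---|
| 1.3 | 4.0 | (1.3 × 1.3 × 4.0)^(1/3) = 1.89 | 1.61 | 1.53 | 1.45 |
| 1.1 | 2.8 | (1.1 × 1.1 × 2.8)^(1/3) = 1.50 | 1.28 | 1.22 | 1.15 |
| 3.0 | 1.0 | (3.0 × 3.0 × 1.0)^(1/3) = 2.08 | 1.78 | 1.68 | 1.60 |

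- Row 1 passes at SD 0.30 and 0.40 although the one-dose ratio is below 1.50. It fails at SD 0.50.
- Row 2 fails, although the two-dose contrast alone (47 vs 47) has lower limit 2.8/1.315 = 2.13 at SD 0.30 and 2.8/1.578 = 1.77 at SD 0.50.
- Row 3 passes throughout with no effect after two doses.

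**What is tabulated by dose.** Template 39 gives adjusted GMCs and ratios to IIV4 for all groups, at Day 29 or Day 85 according to schedule. It adds tables for the two-dose groups at Day 85 and for the pooled cH8-primed groups at Day 29. Dividing an adjuvanted group's ratio to IIV4 by its non-adjuvanted counterpart's gives a by-dose point estimate. The displayed intervals do not give its CI, because the two ratios share the IIV4 reference. Template 36 has rows for the two main effects only.

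**The case against.** The strongest reply is that the pooled contrast is an openly stated design choice. A main-effects average over a three-by-three layout is a recognised way to gain precision. It uses the right sampling day for each regimen, 28 days after the last planned priming dose. The phrase in section 4.2 can also be read as fixing the sampling day for each regimen rather than asking for two estimates. The words on interaction exclude it only from the primary analysis, section 6.2.3.2 allows further ratios if needed, and section 7 calls the comparative analyses descriptive.

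Much of this stands. The pooled rule is not an error. Two stronger readings may tempt a reader and are not supported. One is that the by-dose adjuvant effect cannot be obtained at all: Template 39 and the group GMTs allow a point estimate. The other is that the pooled rule will give the wrong decision: that needs a strong dependence on dose, and the SAP neither states nor suggests one.

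Three things remain. Section 3.2 makes the two-estimate reading of section 4.2 the more natural one. No secondary interaction analysis is described. Leaving a named secondary endpoint to a choice made at the time of analysis is not pre-specification.

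**Conclusion.** The secondary endpoint in section 4.2 has no pre-specified direct estimate or confidence interval at Day 29 or at Day 85. The only adjuvanted versus non-adjuvanted contrast weights the one-dose effect 2/3 and the two-dose effect 1/3, and cannot reveal a difference between them. The weighting follows from equal groups of 47 and the additive model, and will shift slightly if exclusions leave the groups unequal.

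The lower limits rest on assumed SDs and assumed, strongly differing effects. They show that the pooled ratio can mask a difference in either direction. They are not probabilities of a wrong decision. The gap is in what is reported, and it can be closed without changing the decision rule.

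**What to change.** 1. Add to section 6.2.3.2 and Template 41, for anti-H1 stalk ELISA only, descriptive baseline-adjusted GMT ratios with 95% CI for AS03 vs none and AS01 vs none:
   - at Day 29 across all nine SUIV groups, adjusted for the first antigen (about 141 per adjuvant level);
   - at Day 85 within the cH8/5/11 groups (47 per arm).

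   Extend the Template 41 footnote, which now ties Day 29 to one-dose groups only.
2. Report the adjuvant-by-priming-sequence interaction as a supportive analysis.
3. Keep the pooled 94.46% rule. State in section 7 that it is an average over schedules, reported alongside the by-dose ratios, with no additional alpha claimed for them.

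The by-dose ratios should not become a second pass/fail test. At SD 0.3 to 0.6, and with the same critical value, a lower limit above 1.50 needs an observed ratio of 1.76 to 2.06 pooled, but 1.97 to 2.59 at Day 85. Disagreement could therefore reflect sample size alone.

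The cost is SAP wording and a few table rows from samples already planned. The Day 85 interval is about √(141/47) = 1.73 times as wide on the log scale as the pooled one at the same confidence level.

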#### 4.3. Tertiary endpoints

- Evaluation of CMI parameters in terms of frequencies of:
  - Antigen-specific CD4+/CD8+ T-cells identified as producing at least two markers among CD40L, IL-2, TNF- $\alpha$  and IFN- $\gamma$  upon *in vitro* stimulation at Days 1, 29 **and** 85.
  - B-memory cells reactive with the challenge antigen(s) at Days 1, 8, 29, 64 **and** 85.
  - Plasmablasts reactive with the challenge antigens at Days 1, 8 **and** 64.
- Levels of HI antibody to chimeric vaccine strains **cH5/1N1 and cH8/1N1**:  
The following aggregate variables will be calculated with 95% CI:
  - Seropositivity rates and GMTs at Days 1, 29 **and** 85.
  - Seroprotection rate (SPR) at each timepoint listed above.
  - Seroconversion rate (SCR) at Days 29 **and** 85.
  - MGI from Day 1 to each subsequent timepoint listed above.
- Assessment of the *in vivo* protective effect of the anti-stalk antibodies when transferring Day 1 **and** Day 85 pooled serum from all evaluable subjects of each vaccine groups to mice that will be subsequently challenged with cH6/1N5\* or with H1N1 contained in the IIV4, using the following endpoints [refer to Appendix D of the protocol]:
  - Survival over 14 days post-challenge (day of death/euthanasia for weight loss  $> 25\%$  baseline body weight) in groups of 35 mice\*\*/serum pool/vaccine group/timepoint.

- Weight loss (change from baseline over 14 days post-challenge) in groups of 35 mice\*\*/serum pool/vaccine group/timepoint.
- Lung virus titer in TCID50/mg (log10 fold change [Day 1 minus Day 85]), within challenge group.
- Pre- and post-transfer titer of human IgG to cH6/1N5\* by ELISA or HI.
- Pre- and post-transfer titer of human IgG to H1N1 by ELISA or HI.
- Pre- and post-transfer titer of human IgG to recombinant HA protein by ELISA.

\*Or an alternative challenge virus with similar attributes but more fit for purpose.

\*\*If sufficient serum volumes are not available, and depending on the challenge virus pathogenicity, the number of mice can be reduced to as low as 10 mice per timepoint and virus challenge.

**Note:** the passive transfer experiment will be analyzed by the pre-clinical statistical team and is not covered by the present SAP document.

